In a systematic review of available literature in 2014, Likis notes that the most common maternal adverse effects are unpleasant side effects that affect tolerability (e.g., nausea, vomiting, dizziness, and drowsiness). Some of the above listed maternal adverse effects are common in laboring women regardless of whether analgesia is used⁶. We believe administration of nitrous oxide for ECV to be a safe practice with a favorable risk to benefit ratio. Confidence in the safety of this study is bolstered by the long history of safe administration to women in labor.

There are concerns of potential neurotoxicity of nitrous oxide, but this finding is limited to animal studies and only when used in combination with other anesthetics. Nitrous oxide is transmitted via the placenta and is rapidly eliminated by the neonate after birth once breathing begins. No evidence exists to suggest altered neonatal outcomes associated with the use of nitrous oxide alone. Apgar scores in newborns whose mothers used nitrous oxide did not differ significantly from those of newborns whose mothers used other labor pain management methods or no analgesia⁶.

Recently published literature has provided evidence that exposure of the immature animal brain to anesthetics during the period of rapid synaptogenesis triggers rapid neurodegeneration and causes significant long-term cognitive impairment⁸. However, nitrous oxide, by itself at subanesthetic concentrations, triggers little or no neuroapoptosis in the infant rat brain⁹. In our study, nitrous oxide will be delivered at 50%, which is an analgesic or subanesthetic concentration. In addition, no other analgesic or anesthetic agents will be administered in combination with nitrous oxide.

Nitrous oxide is classified as a Class C drug in pregnancy by the US FDA, “Risk cannot be ruled out. Either studies in animals have revealed adverse effects on the fetus (teratogenic or

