Immediately before an ECV attempt participants will breathe through the facemask of the Nitronox device for 30 seconds and will then be free to use the device ad lib during the ECV attempt. Immediately following each attempt, while fetal monitoring is occurring, the participants will be asked to rate their maximum pain score (0-10) during the previous attempt. They will also be asked to rate their current level of anxiety (0-10). This process will be repeated for any further ECV attempts.

At conclusion of all ECV attempts, while fetal monitoring is occurring, the participants will be asked to rate their current level of pain (0-10), their satisfaction with the procedure (0-10) and about any side effects they experienced (nausea, vomiting, dizziness, headache, other). Participants will continue to be monitored on labor and delivery as current protocol dictates, typically 30 minutes of maternal and fetal monitoring if there are no complications and fetal status is reassuring.

Following the procedure, the obstetrician who performed the procedure will be asked to rate how difficult they felt it was to perform the procedure (1-10) and to rate how much they felt the analgesic provided assisted in performing the procedure (1-10). They will also be asked to

indicate whether they thought the patient was in the treatment or placebo arm of the study. This will be recorded to address the adequacy of blinding.

Outcomes that will be recorded following the procedure include whether the procedure was successful, the number of attempts performed, complications associated with the procedure (maternal hypotension, fetal bradycardia transient/persistent, emergent cesarean delivery, cord prolapse, placental abruption, other), eventual mode of delivery, indication for cesarean delivery if performed and analgesic/anesthetic used for delivery if any.

All study variables will be assessed and recorded by one of the study investigators to ensure consistency in data collection.

Study outcome evaluation:

A suite of preliminary tabular and graphical investigations will be conducted prior to quantitative analyses to provide a thorough understanding of the data. These investigations will include:

- a. Descriptive statistics, with histograms and boxplots on continuous variables
- b. Frequency distributions on discrete variables
- c. Correlations among potential model predictors and covariates to reveal potential variable multicollinearity problems.

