In addition to the information compiled from the preliminary investigations described above, Chi-square tests of association for the outcome variables of interest and principle predictors will be conducted to reveal important relationships and justifications for more robust analyses.

The primary outcome of the study is pain experienced during ECV. The null hypothesis of this outcome is that there is no difference in pain scores between patients who use a mixture of 50% nitrous oxide and 50% oxygen during ECV (treatment group) compared to those that use oxygen only during ECV (placebo group). Pain scores during each ECV attempt will be recorded for each participant. For those participants who have more than one attempt these scores will be averaged to obtain a single score for the entire procedure. A student t-test will then be performed to evaluate the null hypothesis of no difference in pain scores between the treatment vs placebo groups. A difference in pain score of 2 (Scale: 0-10) is considered clinically significant. Based on a mean pain score difference of 2 and an average standard deviation of 2.5 for the treatment and placebo groups, a statistical power of 80% is expected. Consideration will be given to categorizing the patients into “Low”, “Moderate” and “Severe” pain score categories along clinical guidelines to further assess the impact of analgesia on pain severity. Where feasible, both p-values and confidence intervals for odds ratios from logistic regression and/or parameter estimates from general linear modeling will be reported.

Secondary outcomes of the study include patient anxiety experienced during the ECV procedure, pain scores following the ECV procedure, patient satisfaction with ECV procedure, side effects experienced and OB providers ratings of ease of procedure.

We will be recording whether the ECV procedures are successful and whether any complications occur as a result of the ECV procedure, but given that our study is powered to evaluate patient pain and not these outcomes we do not expect to see any differences. Previous studies have shown that analgesia alone does not alter success rates of ECV, this includes a previous study that used nitrous oxide during ECV.

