The only area where we might expect to have missing data is for delivery information and type of anesthetic used for delivery since not all patients who have an ECV at UNC actually deliver at UNC. However, this data is included on the data sheet only because we are curious to know whether involvement in the study might influence participants to try nitrous oxide for labor analgesia. The use of nitrous oxide for labor, while common worldwide, remains uncommon in the United States. Many women who present in labor have actually never heard of the use of nitrous oxide for labor analgesia. We also have parturients who come to UNC to deliver specifically because we offer nitrous oxide for labor analgesia. It would be interesting to know whether our contact with them through the consent process may inform them of and potentially lead them to consider use of nitrous oxide for labor analgesia.

Power analysis:

A power analysis to determine the sample size required to see a difference in pain score of 2 between the groups was performed which yielded the needed sample size of 50. This analysis

was based on pain scores from previous studies on pain during ECV in the setting of no analgesia as well as use of nitrous oxide or remifentanil for treatment of pain (Burgos et al, Fok et al, Munoz et al).

Normal Distribution $\alpha=0.05$	
Mean Difference	2
Standard Deviation	2.4
Total Sample Size	50
Number of Sides	2
Power	0.823

Lognormal Distribution $\alpha=0.05$	
Group 1 Geometric Mean	4.5
Group 2 Geometric Mean	6.5
Coefficient of Variation	0.45
Total Sample Size	50
Number of Sides	2
Power	0.843

Data handling:

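### Drowsiness, which the protocol cites among the most common effects of nitrous oxide, is not a named item in the side-effect question and may be under-recorded

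*Combined protocol and SAP*

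**What the plan says.** Three places in the combined protocol and SAP bear on this.

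- **Background and Purpose.** Citing a systematic review of nitrous oxide in labor, it says that "the most common maternal adverse effects are unpleasant side effects that affect tolerability (e.g., nausea, vomiting, dizziness, and drowsiness". It adds a caveat: "Some of the above listed maternal adverse effects are common in laboring women regardless of whether analgesia is used".
- **Study Procedures, ratings after the last attempt.** Participants are asked "about any side effects they experienced (nausea, vomiting, dizziness, headache, other".
- **Study outcome evaluation.** The secondary outcomes include "side effects experienced and OB providers ratings of ease of procedure".

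The separate list of procedural complications in Study Procedures (maternal hypotension, fetal bradycardia, emergent cesarean, cord prolapse, abruption, other) has no item for drowsiness or sedation. Study outcome evaluation also says that all data come from a single interaction with each woman, with no contact afterwards.

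**The concern.** The background list and the question overlap on nausea, vomiting and dizziness. Drowsiness appears only in the first and headache only in the second, and no reason is given for either difference. An effect that the protocol expects is therefore recorded only through an open category, while the others have a line of their own.

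At stake is the tolerability part of the trial's answer. The Background section hopes that the results will encourage use of nitrous oxide for ECV, for other painful procedures and outside obstetrics, so the side-effect table will be read alongside the pain result. If women report named symptoms more readily than unnamed ones, the drowsiness rate would be measured to a lower standard than the rates beside it. A comparison of arms on that symptom would be weakened, and with a single interaction there is no later chance to recover it.

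**Working it through.** **Step 1. Set the two lists side by side.**

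| Effect | Example in Background | Named in the question |
|---|---|---|
| Nausea | yes | yes |
| Vomiting | yes | yes |
| Dizziness | yes | yes |
| Drowsiness | yes | no (open category only) |
| Headache | no | yes |

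Three of four examples carry over. The background list is introduced as examples, so it is neither closed nor ranked. The question covers any side effect, so drowsiness is in scope and can be recorded.

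**Step 2. What a loss would do.** Let p1 and p0 be the true proportions with drowsiness on nitrous oxide and on oxygen, and c the share of cases that reach the form, taken as equal in both arms. The expected recorded difference is c × p1 − c × p0 = c × (p1 − p0). The ratio of the two proportions is unchanged, but the absolute difference shrinks by the factor c. With c = 1 nothing is lost. The documents give no value for p1, p0 or c.

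**Step 3. Illustration on assumed counts.** The Power analysis section gives 50 women in total. No allocation ratio is stated, so 25 per arm is an assumption. The true counts (10 versus 2) and the values of c are also assumptions. Expected counts are rounded to whole women and compared by two-sided Fisher exact test.

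| Share recorded (c) | Nitrous oxide | Oxygen | p |
|---|---|---|---|
| 100% (no loss) | 10/25 | 2/25 | 0.018 |
| 60% | 10 × 0.6 = 6/25 | 2 × 0.6 = 1.2, so 1/25 | 0.10 |
| 40% | 10 × 0.4 = 4/25 | 2 × 0.4 = 0.8, so 1/25 | 0.35 |
| 20% | 10 × 0.2 = 2/25 | 2 × 0.2 = 0.4, so 0/25 | 0.49 |

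The first row is a favorable starting point. With complete recording, 8/25 versus 2/25 gives p=0.074 and 5/25 versus 1/25 gives p=0.19.

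**Step 4. The same in terms of power.** Assume 25 per arm, drowsiness of 4% on oxygen, and a two-sided Fisher test at 0.05.

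| True rate on nitrous oxide | Expected cases, c = 1 | Power, c = 1 | Expected cases, c = 0.5 | Power, c = 0.5 |
|---|---|---|---|---|
| 20% | 25 × 0.20 = 5.0 | 0.23 | 2.5 | 0.02 |
| 30% | 25 × 0.30 = 7.5 | 0.61 | 3.75 | 0.12 |
| 40% | 25 × 0.40 = 10.0 | 0.86 | 5.0 | 0.30 |

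These tables show only how the result depends on recording. They are not evidence that a loss will occur, nor of how large it would be.

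**Step 5. What is untouched.** The primary outcome is the pain score, and the sample size rests on a pain difference of 2. Neither uses side-effect data.

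**The case against.** The strongest case on the other side has four parts.

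*The question is open.* It asks about any side effect and ends with an 'other' category, so drowsiness can be recorded. The protocol does not say that the listed items are read out. They may be recording categories for an open question, in which case all symptoms are elicited alike and the contrast between prompted and unprompted items disappears. **This stands**, and it makes the point conditional. The data sheet is not among the documents, so whether it already lists drowsiness cannot be checked.

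*The background evidence is about labor.* Its list gives examples without rates, and the protocol notes that some of these effects occur in labor without analgesia. It also describes ECV pain as lasting under 5 minutes and the gas as having a rapid offset. How much drowsiness to expect here is unknown. **This stands** against calling drowsiness a main effect in this setting. It does not argue against asking: the oxygen arm can separate drug effect from background only if the symptom is recorded reliably in both arms.

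*Recording is even-handed.* The plan states: "All study variables will be assessed and recorded by one of the study investigators to ensure consistency in data collection". The investigators are to be masked to the gas. **This stands** against a suggestion of biased recording between arms. It does not remove the shrinkage in Step 2, which arises even when the loss is equal.

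*No planned inference is lost.* The trial is powered on pain, and no test of individual side effects is specified. **This stands**, and it is a reason to treat the point as minor.

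A reader might infer that the plan is bound to under-count drowsiness, or that nitrous oxide will look better tolerated than it is. The documents do not support either inference: they leave open how the question is put, and they give no rate for the symptom or for its reporting.

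**Conclusion.** The mismatch between the two lists is plain on the text, and no other part of the plan collects drowsiness. The consequence is conditional. If the named items are prompted, drowsiness may be under-recorded, its rate would not be comparable with theirs, and nitrous oxide could look better tolerated on this secondary outcome. If nothing is lost through the open category, or if all symptoms are elicited alike, the comparison is unharmed.

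The size of any loss cannot be derived from the documents. The p-values and power figures above rest wholly on assumed rates, assumed reporting shares and an assumed equal split of the 50 women. The primary pain analysis and the sample size are unaffected. This is a minor point with a nearly free remedy, not a contradiction in the plan: nothing in it promises to collect every effect cited in the background.

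**What to change.** In Study Procedures and on the data sheet, extend the list to nausea, vomiting, dizziness, drowsiness, headache, other. State that each named item is asked the same way of every woman in both arms, and report each by arm. Say briefly how entries under 'other' are coded. If the data sheet already lists drowsiness, bring the protocol text into line with it.

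The cost is one more item on the form, with no extra visit or staff. The recorded side-effect rate may come out less favorable to nitrous oxide.

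### Do the two planning SDs (2.5 and 2.4), and a lognormal power figure beside them, undermine the sample size of 50?

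*Combined protocol and SAP*

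**What the plan says.** The relevant text is in two sections of the combined protocol and SAP.

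- **Study outcome evaluation** sets the primary analysis: "A student t-test will then be performed to evaluate the null hypothesis of no difference in pain scores between the treatment vs placebo groups". Scores from several attempts are first averaged within each woman. The target is stated as "A difference in pain score of 2 (Scale: 0-10) is considered clinically significant". The inputs to the power sentence follow: "Based on a mean pain score difference of 2 and an average standard deviation of 2.5 for the treatment and placebo groups". The plan attaches a round figure of 80% to them, and gives neither a sample size nor a method of calculation there.
- **Power analysis** says that the calculation for a difference of 2 "yielded the needed sample size of 50". Its normal-distribution table lists "Standard Deviation 2.4", two sides, alpha 0.05, a total of 50 and power 0.823. A second table, labelled lognormal, lists geometric means of 4.5 and 6.5, a coefficient of variation of 0.45, a total of 50 and power 0.843.

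The plan does not say why the SDs differ, or which calculation governs the sample size. No log transformation of the pain score is planned.

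**The concern.** One test, one target difference and one trial carry two SDs and three powers (80%, 0.823 and 0.843). Someone who puts the SD of 2.5 into the method behind the normal table finds that 50 women give a little under 80%, and that 52 would be needed. The 0.843 belongs to a comparison of log scores, whereas the planned t-test uses raw scores. The lognormal model also fits a 0-10 scale poorly: it puts about 16% of the group with geometric mean 6.5 above 10, and it cannot produce a score of 0.

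If the shortfall were material, the trial would be sized on the more favourable of two variance assumptions, with nothing in reserve for a woman without a pain score.

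**Working it through.** **Inputs.** Difference 2, two-sided alpha 0.05 and total 50 come from the plan, as do SD 2.4 (Power analysis) and SD 2.5 (Study outcome evaluation). Equal allocation, 25 per arm, is an assumption; it reproduces both table powers.

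**1. The normal table.** The noncentrality is difference / (SD × √(2/n)), with 48 degrees of freedom.

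- SD 2.4: 2 / (2.4 × √(2/25)) = 2 / 0.679 = 2.95. Power from the noncentral t is 0.8230, which matches the stated 0.823.
- The normal approximation at SD 2.4 gives 0.838, so this table was computed with the t distribution.

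**2. The 80% sentence, SD 2.5.**

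- Noncentrality: 2 / (2.5 × √(2/25)) = 2 / 0.707 = 2.83. The noncentral t gives 0.7915 (79.1%).
- Normal approximation: Φ(2.83 − 1.96) = 0.807.
- Sample size by the normal approximation: 2 × (1.96 + 0.842)² × 2.5² / 2² = 24.5, rounded up to 25 per arm, or 50 in total.

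The two usual methods give 79.1% and 80.7%, one on each side of the stated 80%.

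**3. How far the SD can move.** By the exact t calculation:

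| Total N | SD 2.4 | SD 2.5 |
|---|---|---|
| 46 | 78.9% | 75.6% |
| 48 | 80.7% | 77.4% |
| 50 | 82.3% | 79.1% |
| 52 | 83.8% | 80.8% |

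With 50 women, power stays at 80% or more up to an SD of 2.47.

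**4. The lognormal table.**

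- Log-scale SD: √(ln(1 + 0.45²)) = 0.429. Log difference: ln(6.5/4.5) = 0.368.
- The noncentral t with 25 per arm gives 0.8429, which matches the stated 0.843.
- The planned raw-score t-test was simulated under the same inputs. Power was 0.811 in 200,000 trials, and about 0.83 in separate runs with scores capped at 10.

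Each of the three stated powers follows from its own inputs. Under the lognormal inputs the planned test still exceeds 80%.

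**The case for a change.** The best case for a correction has three parts.

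**Method.** The normal table is t-based. Rescuing the 80% with a normal approximation therefore means that the plan used two methods as well as two SDs. By one consistent method, SD 2.5 gives 79.1% and needs 52 women. This is arithmetically right. However, the method is established only for the table; the 80% sentence names none and is plainly a round figure. A gap of 0.9 points is also smaller than the uncertainty in any planning SD taken from other studies.

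**The lognormal row.** It does not describe the planned analysis. Its inputs imply raw means of 4.93 and 7.13, a difference of 2.19 rather than 2, with SDs of 2.22 and 3.21. That is so, but the table is labelled as lognormal and nothing attributes 0.843 to the raw-score t-test. It reads as a check under a skewed distribution, and that check supports 50. Its poor fit at the ends of the scale is a matter of degree: a normal model with mean 6.5 and SD 2.5 puts about 8% above 10, since (10 − 6.5)/2.5 = 1.4.

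**Margin.** With 46 evaluable women, power would be 78.9% or 75.6%. The figure of 46 is an assumption with no basis in the plan. Pain is rated immediately after each attempt, and Study outcome evaluation expects gaps only in the delivery information. At SD 2.4, 48 women suffice, so the calculation that produced the sample size has two to spare.

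What stands is that the SDs differ without explanation.

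**Conclusion.** The inconsistency is real, but correcting it would bring no gain. With equal allocation assumed, 50 women give 82.3% power at SD 2.4 and 79.1% at SD 2.5 by the exact t calculation. Both fit a design described as having roughly 80% power, and the largest departure from the stated 80% is 0.9 points on the low side. The sample size is tied to the table that uses SD 2.4, and that table reproduces exactly.

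Neither planning SD enters the primary t-test, which uses the variance observed in the trial, so the type I error, the estimate and its interval do not depend on which figure is kept. Anyone reporting the trial can quote the table's inputs with the sample size they produced. No change to the plan follows.

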Complications of ECV are very rare. Given that nitrous oxide has been demonstrated to be safe for labor analgesia, a similar patient population to ours, we do not anticipate that we would be able to detect any differences in complications in this patient population. These variables are being recorded for completeness.

Several variables known to influence the effectiveness of ECV (BMI, age, ethnicity, gestational age, parity, placentation, type of breech position, amniotic fluid level, tocolytic used, history of prior c-section) are being recorded for each participant. We are also recording whether participants have previously undergone ECV with a prior pregnancy since this could influence their expectations of this procedure. These variables will be analyzed using chi-square or fisher exact test to ensure that there are no differences in these variables between the treatment and placebo groups.

Either a general linear model or a logistic model will be employed to assess the effect of the main effects, interactions, and appropriate covariates on the primary outcomes of interest. Selected covariates and potential confounders will be included in a “forward” regression model and subsequently retained in the final model only if found to explain a significant amount of the variability in the outcome. Candidate covariates include patient anxiety during the ECV procedure, patient satisfaction, ECV success and history of previous ECV.

All data will be recorded during one interaction with the participants and will not require participants to be contacted following the ECV procedure. Because of this the likelihood of missing data and drop out is extremely low.

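### The baseline significance tests cannot ensure balance with about 25 women per arm, and the covariate model for pain selects by p-value from candidates mostly recorded after treatment has begun

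*Combined protocol and SAP*

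**What the plan says.** All of this stands in the combined protocol and SAP, mainly under Study outcome evaluation.

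- **Primary analysis.** Pain scores are averaged over attempts within each woman. "A student t-test will then be performed to evaluate the null hypothesis of no difference in pain scores". No covariate enters this test.
- **Baseline comparison.** The plan introduces "Several variables known to influence the effectiveness of ECV" and names ten: BMI, age, gestational age, ethnicity, parity, placentation, breech type, amniotic fluid, tocolytic and prior caesarean. It adds an eleventh: "We are also recording whether participants have previously undergone ECV with a prior pregnancy", on the ground that this could affect expectations. Then: "These variables will be analyzed using chi-square or fisher exact test to ensure that there are no differences in these variables".
- **Covariate model.** A general linear or logistic model is planned for the primary outcomes. Entry is by forward selection, and a covariate is "retained in the final model only if found to explain a significant amount of the variability in the outcome". The plan goes on to name four, without closing the list: "Candidate covariates include patient anxiety during the ECV procedure, patient satisfaction, ECV success and history of previous ECV".

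Study Procedures fixes the timing. Anxiety is asked after each attempt and satisfaction after the last attempt. Success is recorded after the procedure. Anxiety and satisfaction are also listed as secondary outcomes.

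**The concern.** The plan gives the balance tests a job they cannot do. A non-significant result in a small trial says little about how alike the arms are, and a significant one after sound randomisation is a chance event. Read as written, the rule would let a sizeable imbalance be reported as no difference.

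The model is the more consequential part. It is where adjustment would happen, yet three of its four named candidates are variables that the gas may change, or that pain itself may change. Satisfaction is the clearest case: a woman who had less pain is likely to report more satisfaction. Adjusting pain for it can remove part of the treatment effect or otherwise distort it. Retention by significance makes this more likely, because variables closely tied to pain are the ones most likely to be kept. The plan says that parameter estimates from such models will be reported where feasible, so the distorted estimate could appear beside the t-test.

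**Working it through.** **Inputs.** From Power analysis: total N=50, difference 2, SD 2.4, two-sided alpha 0.05, power 0.823. From Study outcome evaluation: SD 2.5 with power 80%. Assumed: 1:1 allocation, so n=25 per arm. Also assumed, because the documents give no figure: the share R² of pain variance explained by covariates, taken as 0, 5, 10 and 20%.

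**1. The plan's own power.** SE = 2.4 × √(2/25) = 0.679. Noncentrality = 2/0.679 = 2.946 on 48 df, critical value 2.011. Power = 0.823, as stated. With SD 2.5, SE = 0.707, noncentrality = 2.828 and power = 0.791, close to the 80% in the text. The power figures are not in error, and the match supports 25 per arm.

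**2. What the balance tests can see.** For 15/25 against 10/25:

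- Uncorrected chi-square = 50 × (15×15 − 10×10)² / 25⁴ = 50 × 15,625 / 390,625 = 2.0, p=0.16.
- Fisher exact p=0.26.

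With 5 to 12 of 25 in the lower arm, significance needs a gap of 7 women (28 points) by chi-square or 8 women (32 points) by Fisher. A gap of 20 to 24 points therefore passes. For a factor carried by half of the women, randomisation alone gives a gap of 20 points or more with probability 0.20.

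**3. What such a gap could do.** Shift in the estimated difference = imbalance × effect of the factor on pain. If the factor moves pain by 1 to 2 points (an assumption), the shift runs from 0.20 × 1 = 0.2 to 0.24 × 2 = 0.48 points, against a target of 2.

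**4. Timing of the named candidates.**

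| Candidate | When recorded | Pre-treatment? |
|---|---|---|
| Previous ECV | At enrolment | Yes |
| Anxiety | After each attempt | No |
| Satisfaction | After the last attempt | No |
| ECV success | After the procedure | No |

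**5. Why the last three matter.** In a linear model with one covariate, adjusted difference = raw difference − b × (covariate difference between arms), where b is the within-arm slope of pain on the covariate. For a pre-treatment covariate, randomisation makes the expected covariate difference zero. For anxiety, satisfaction or success it need not be zero, because the gas may act on them, so the adjusted figure no longer estimates the whole effect on pain. The documents give neither b nor the covariate difference, so no size can be put on this.

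**6. What two fixed pre-treatment covariates would cost or gain.** With k covariates, SE = SD × √(1−R²) × √(2/25) × √(1 + k/(47−k)), on 48−k df. The last factor is an approximate charge for estimating the covariate slopes. For k=2 it is √(1 + 2/45) = √1.0444. At SD 2.4 and R²=0, SE = 0.679 × √1.0444 = 0.694, noncentrality = 2.883 on 46 df, power = 0.806.

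| Assumed R² | Power, SD 2.4 | Power, SD 2.5 |
|---|---|---|
| Unadjusted | 82.3% | 79.1% |
| 0 | 80.6% | 77.3% |
| 5% | 82.5% | 79.4% |
| 10% | 84.5% | 81.5% |
| 20% | 88.4% | 85.7% |

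Break-even for two covariates lies at an R² of about 4.4%.

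**The case against.** The strongest reply is that the primary test is untouched. Under sound randomisation the unadjusted t-test is valid, and its type I error already allows for chance imbalance. That stands. Baseline adjustment is a matter of precision and of the estimate in this one trial; step 3 puts that shift at no more than about half a point under its assumptions.

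Four stronger readings are tempting, and the documents do not support them.

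- **That the listed variables are known to predict pain.** The plan ties them to the effectiveness of ECV. Nothing in it says that BMI, parity or the others predict pain.
- **That they are barred from adjustment.** The model text allows selected covariates and potential confounders, and the candidate list is open. Their use is unspecified, not excluded.
- **That the plan gives up power that adjustment would supply at no cost.** With three covariates at SD 2.4 and R²=5%, power is 81.6%, below the unadjusted 82.3%. Any gain depends on an R² that the documents do not give.
- **That the tests both miss large gaps and raise many false alarms.** A split of 16/25 against 9/25 passes Fisher (p=0.089) but is flagged by uncorrected chi-square (p=0.048). Eleven independent tests of exact 5% size give 1 − 0.95¹¹ = 43% chance of a false difference. Fisher's actual size here is about 0.9% at 10% prevalence and 3.3% at 50%, which gives roughly 9 to 31%. Fisher's weak detection and the 43% do not belong to the same test.

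The plan also already calls for descriptive statistics and frequency tables, so part of the remedy exists, though not stated as by arm.

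**Conclusion.** The point holds in two parts. First, the balance tests cannot ensure what they are meant to ensure: gaps of 20 to 24 percentage points pass either test across most of the range, and for three continuous variables the tests named need cut-points that are not given. Second, the covariate model names three post-treatment variables out of four and keeps covariates by significance, so its estimate of the effect on pain can be distorted by an amount that the documents do not allow one to size.

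The primary t-test and the stated power are sound. The conclusion rests on 1:1 allocation, which is inferred. The power figures for the remedy rest on assumed R² values. This should be corrected before analysis, but it does not undermine the main comparison.

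**What to change.** - Drop the p-values for baseline variables. Show each by arm, as mean and SD or as number and percentage.
- In the linear model for pain, replace forward selection with randomised arm plus one or two pre-treatment covariates, named in advance because they are expected to predict pain and kept whatever their p-value or the observed balance. Previous ECV and parity are examples already collected at enrolment. They overlap, since an ECV in a prior pregnancy implies a prior pregnancy, and the investigators should give their reason for expecting each to matter for pain.
- State that no variable recorded after randomisation will be a covariate. This removes anxiety, satisfaction and ECV success. The tocolytic also needs a decision, because Study Procedures describes it after randomisation although before the gas.
- State whether the t-test or this model is the primary analysis.

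This is a change of wording only and needs no new data. The cost with two covariates is about 2 points of power if they explain nothing; above an R² of roughly 5% there is a gain.
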